## 13.2 Definitions of (S)AEs and reporting

This is a study using three devices to measure plantar load, with no instigation of treatment, nor change to patients' standard care. Therefore, incidents will only be reported as AEs or SAEs if injury occurs during walking assessment.

## 14. Outcomes

### Primary outcome:

The primary outcome is the difference in peak plantar strain and peak PSS between the DFU and Low risk groups as measured by:

- 1) STAMP
- 2) SLIPS

### Secondary outcomes:

- 1) Regional peak plantar strain as measured in-shoe using the STAMP insole. Measured at the standard ten regions heel, mid foot, 1st MTH, 2nd MTH, 3rd MTH, 4th MTH, 5th MTH, hallux, second toe and toes 3-5. Mean regional peak plantar strain will be compared between DFU and Low risk groups.
- 2) Regional peak PSS measured at the standard ten regions heel, mid foot, 1st MTH, 2nd MTH, 3rd MTH, 4th MTH, 5th MTH, hallux, second toe and toes 3-5. Mean peak regional PSS will be compared between DFU and Low risk groups.
- 3) Global and regional peak plantar pressure, and PTI measured in-shoe using the Pedar system, compared between DFU and Low risk groups.

## 15. Statistical considerations

### Sample size

The STAMP method is a novel technique, as such nil data exists in the literature to determine a sample size. SLIPSTREAM is a preliminary study and due to the time and resource constraints of an MD project it is not expected to be powered to detect statistical significance. Based upon preliminary work, it is expected the mean difference will be 4, with a standard deviation of 6. Therefore 28 patients per group are required for 90% significance at a power of 80%.

## Planned recruitment rate

It is estimated 4 patients are identified with a healed plantar ulcer every week at the DLSS clinic. Assuming half of these consent to inclusion, and dependent upon the required sample size, recruitment is likely to be completed within one year.

# 16. Statistical analysis

## Primary outcome analysis

The mean changes in coordinates and magnitude of principle strains on the plantar aspect of the foot will be calculated for each patient using GOM correlate and MATLAB. Linear regression will be used to compare mean peak plantar strain between DFU and Low risk groups. Bivariable analysis using Pearson's correlation coefficient will be performed to investigate the relationship between the continuous independent variables and mean peak plantar strain. Multiple regression analysis will be used to explore the relationship between correlated continuous variables and the risk group.

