The authors have performed a systematic review and meta-analysis to summarise the literature on PSS in the diabetic foot. The results of this meta-analysis demonstrated that patients with diabetes and with a loss of protective sensation sustain greater levels of PSS than healthy controls. It also showed those with a current, or previous ulcer exhibit significantly greater levels of PSS compared with those with loss of protective sensation without a history of ulceration. However, it also identified a wide spectrum of methods of measuring PSS, with no validated gold standard. Most studies were performed 'barefoot'; however, as the cornerstone of management of the diabetic foot is ensuring plantar tissue stress reduction through all weight bearing activities by using appropriate footwear, this form of analysis does not reflect the typical shear stresses that are sustained during a normal day. The review therefore highlighted the need for advances in technology to reliably measure 'in-shoe' shear stress and to transfer this to clinical studies investigating its relationship with ulcer formation.

Sensing platforms and insoles measure PSS and plantar pressure in real-time at the foot-surface interface. The technical challenges involved has led to the development of a new method of measuring the effects of PSS and plantar pressure at the foot-surface interface based upon Digital Image Correlation (DIC). DIC is an optical based technique used to measure displacement and strain. It involves comparing the image of the point or object of interest prior to loading, with those after or during loading. The method utilises DIC software employing algorithms to track blocks of pixels to measure displacement or strain. Strain is defined as the ratio between the deformation of a structure and its original length. In the context of an insole, the strain is determined by the plantar load, the product of both PSS and plantar pressure. Thus, it is hypothesised that the level of strain is a product of the cumulative effect of plantar pressure and shear stress during walking.

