#### SLIPS assessment inclusion criteria

The SLIPS insole has been designed to measure the plantar load of the right foot, and due to its size, can only be accommodated by a size 8-11 shoe. The insole is also only able to accommodate patients weighing <100kg. Therefore, in addition to the above criteria, patients will undergo SLIPS assessment if they fulfil the following additional inclusion criteria:

- 1) Recently healed plantar DFU located on the right foot
- 2) The right foot can be accommodated in a size 8-11 shoe
- 3) Weight <100kg

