## **9. Matching**

Matching of DFU and Low risk groups will not be performed.

Rationale:

In a study by Yavuz et al., (2014), investigating PSS in neuropathic and non-neuropathic patients with diabetes, neither BMI nor age accounted for a significant proportion of the variance of shear between groups.

Furthermore, the effect of age, BMI, gender and walking speed can be adjusted for if appropriate in the analysis.

To ensure equal group sizes for SLIPS assessment, the proportion of patients per group will be monitored and selective sampling according to shoe size and weight will be performed and recruitment adjusted as appropriate.

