## Secondary outcome analyses

- 1) Regional analysis: A masking algorithm will be utilised to map the previously defined areas of interest (Measured at the standard ten regions heel, mid foot, 1st MTH, 2nd MTH, 3rd MTH, 4th MTH, 5th MTH, hallux, second toe and toes 3-5) following data acquisition. Intergroup comparisons will be performed comparing mean peak plantar strain at each region using linear regression. Multiple regression analysis will be used to explore the relationship between correlated continuous variables and the risk group. This method will also be utilised to perform regional intergroup comparisons for peak PSS, peak plantar pressure and PTI.
- 2) Peak PSS between DFU and Low risk groups will be compared using linear regression. Bivariable analysis using Pearson's correlation coefficient will be performed to investigate the relationship between the continuous independent variables and mean peak plantar strain. Multiple regression analysis will be used to explore the relationship between correlated continuous variables and the risk group. This method will also be used to perform comparisons between groups for peak plantar pressure and PTI.
- 3) Multinomial regression analysis will be used to investigate the relationship between peak plantar strain and ulcer location.
- 4) ~~Regional analysis: A masking algorithm will be utilised to map the previously defined areas of interest (Measured at the standard ten regions heel, mid foot, 1st MTH, 2nd MTH, 3rd MTH, 4th MTH, 5th MTH, hallux, second toe and toes 3-5) following data acquisition. Intergroup comparisons will be performed comparing mean PSS at each region using ANCOVA, adjusting for factors matched..... Evidence of associated will be present if  $r > 0.3$ . Multiple regression analysis will be used including continuous variables with  $r > 0.3$ , risk group and the presence of joint deformity.~~

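### In section 16 the adjusted model for peak PSS relates its covariates to strain instead of PSS, and no adjusted model has named covariates or a stated way in for sex.

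*Combined protocol and SAP*

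**What the plan says.** Section 9 (Matching) rules out matching and gives two reasons. The first is a cited study of neuropathic and non-neuropathic patients in which "neither BMI nor age accounted for a significant proportion of the variance of shear between groups". The second is that "the effect of age, BMI, gender and walking speed can be adjusted for if appropriate in the analysis".

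Section 16, Primary outcome analysis, has three steps for strain:

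- a linear regression comparing the groups;
- Pearson correlations of unnamed continuous variables with strain;
- a further model: "Multiple regression analysis will be used to explore the relationship between correlated continuous variables and the risk group".

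Section 16, Secondary outcome analyses, item 2, repeats these steps for peak PSS. The group comparison there is on PSS, but the correlation step examines "the relationship between the continuous independent variables and mean peak plantar strain". The item ends: "This method will also be used to perform comparisons between groups for peak plantar pressure and PTI".

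Section 14 makes peak PSS part of the primary outcome: "The primary outcome is the difference in peak plantar strain and peak PSS between the DFU and Low risk groups". Its analysis nevertheless sits under the secondary analyses.

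Section 11.1 collects age, sex, weight and height. Recording of walking speed is stated in section 11.3 (STAMP) and is not mentioned in 11.4 (Pedar) or 11.5 (SLIPS).

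**The concern.** The study is non-randomised and unmatched. The DFU group comes from secondary-care limb salvage clinics and the Low risk group from community podiatry, so differences in age, sex or body size are plausible, although the documents give no figures. The multiple regression is the only place where the analysis controls for them, and it is loosely defined in three ways.

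- **Wrong outcome.** A covariate matters for the PSS comparison if it relates to PSS. Item 2 judges it by its relation to strain, and carries this over to pressure and PTI.
- **Choice from the data.** If observed correlation decides entry, a real confounder can be left out by chance. The only cut-off in the section, r > 0.3, is in struck-through text, so none is in force.
- **Sex.** Both the correlation step and the model wording are confined to continuous variables. Section 9 lists gender as adjustable, but section 16 gives it no way in.

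At stake is whether the adjusted estimates remove the confounding they are meant to remove. The study is also meant to inform later prospective work (secondary objective 3), which will read those estimates.

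**Working it through.** **1. The plan's own figure.** Section 15 gives a difference of 4, SD 6, 90% significance and 80% power. Reading this as two-sided alpha 0.10:

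n = 2 × (1.645 + 0.842)² × (6/4)² = 2 × 6.18 × 2.25 = 27.8, so 28 per group.

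This matches. With the t distribution the requirement is 28.5 (29), and 28 per group gives 79% power. The figure is for an unadjusted comparison and is not in dispute.

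**2. Outcome against correlation target**

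| Outcome | Group comparison on | Covariates correlated with |
|---|---|---|
| Strain (primary analysis) | strain | strain |
| Peak PSS (item 2) | PSS | strain |
| Peak plantar pressure, PTI (item 2, same method) | pressure, PTI | strain |

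**3. Assumptions for the size.** The documents give no imbalance or correlation, so all of these are assumed: 28 v 28, SD 6, two-sided alpha 0.10, one confounder *d* SD apart between groups with within-group correlation *r* to the outcome. Two entry rules were tried: p < 0.05 (|r| > 0.263 at n = 56) and |r| > 0.3. False-positive rates do not depend on the value of the SD, so they carry over to the PSS scale.

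**4. Unadjusted benchmark, no true difference.** Bias = d × r × SD = 0.8 × 0.3 × 6 = 1.44 units. SE = 6 × √(2/28) = 1.60. The ratio is 0.90, and the noncentral t with 54 df gives 23% false positives.

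**5. Strain, correlated with its own outcome (simulation, no true difference).** Over d = 0.4-1.2 and r = 0.2-0.4, residual bias is 0.05-0.52 units with 10-12% false positives (p < 0.05 rule), or 0.11-0.71 units with 10-13% (|r| > 0.3 rule). At d = 0.8, r = 0.3 the confounder is dropped in 31% or 42% of runs. If a confounder of that size masked a true difference of 4, power would be 57-61% against 77% with fixed adjustment, but nothing in the documents points to masking.

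**6. Peak PSS, covariates judged on strain (simulation, no true PSS or strain difference, d = 0.8, r = 0.3 to PSS)**

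| Adjusted model | False positives |
|---|---|
| Judged on strain, r to strain 0.3 | 12-15% |
| Judged on strain, r to strain 0.2 | 16-20% |
| Judged on strain, r to strain 0-0.1 | 20-23% |
| Judged on PSS itself | 11-12% |
| Covariate always entered | 10% |

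At d = 0.4 all are 10-13%. If strain truly differs by 4 in the same direction, the first three rows become 10-11%, 12-15% and 16-22%. SLIPS numbers are not stated: with 20 per group assumed, the rates are 12-14% (r to strain 0.3) and 19% (r = 0); with 14 per group, 11-14% and 15-16%.

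**7. Sex left out.** Bias = imbalance × effect × SD. A 25-point imbalance and 0.5 SD effect give 0.25 × 0.5 × 6 = 0.75 units; 10 points and 0.3 SD give 0.10 × 0.3 × 6 = 0.18. Simulation gives 0.17-0.74 units and 10-14% false positives.

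**8. Price of fixed adjustment.** With three covariates each d SD apart, variance inflation is 1 + 3d²/4, which is 1.12 at d = 0.4 and 1.48 at d = 0.8. If they explain no outcome variance, SE = 1.604 × √1.12 = 1.70 or 1.604 × √1.48 = 1.95. Power for a difference of 4 on 51 df is 75% or 65%. It is 80% or 70% if they explain 12% of the variance, and 86% or 77% if they explain 27%.

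**The case against.** The strongest objection concerns reach. A reader might infer that the strain-based step distorts the primary PSS comparison. The text does not support this: for strain and PSS alike, the planned group comparison is a plain linear regression, the correlations come after it, and the multiple regression is described as exploratory. A reader might also infer that section 9 made a promise that section 16 breaks. It did not: section 9 permits adjustment where appropriate, and age, BMI and walking speed could still enter as continuous variables. Both limits stand.

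Further points carry weight. That correlation decides entry is an inference, and both cut-offs used above are assumptions. The effect for strain is small. Selection on the correct outcome removes most of the confounding (11-12% against 23% unadjusted at 0.8 SD). The top of the PSS range needs a confounder of PSS nearly unrelated to strain, while section 4 holds that "the strain is determined by the plantar load, the product of both PSS and plantar pressure". In the SLIPS subset the weight limit ("The insole is also only able to accommodate patients weighing <100kg") may narrow any BMI imbalance. Item 2 repeats the strain sentence from the primary analysis, so a copying slip is likely. Section 15 also calls the study preliminary and not expected to be powered.

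None of this removes the point. A slip still has to be corrected. Low power does not make an undefined model easier to interpret. The cited study, as section 9 describes it, covers age, BMI and shear, and is not said to cover strain, sex or walking speed.

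**Conclusion.** The point holds for the adjusted models only. As written, covariates for peak PSS, peak plantar pressure and PTI are related to the wrong outcome. On the natural reading, all covariates are chosen from the data and sex has no stated entry. The unadjusted comparisons are unchanged.

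The size rests on imbalances the documents do not give. With no true difference and a nominal 10%, it is small for strain (10-13% false positives). For PSS it runs from 10-13% at 0.4 SD imbalance to about 12-23% at 0.8 SD with r 0.3 to PSS. At the top of that range the adjustment does almost nothing, since the unadjusted figure is about 23%. This should be put right before analysis; it does not invalidate the planned comparison.

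**What to change.** 1. Correct section 16, Secondary outcome analyses, item 2, so that covariates are related to peak PSS, peak plantar pressure or PTI itself. This costs nothing.
2. For each outcome, report beside the unadjusted estimate one pre-specified linear regression on group with age, sex and BMI, entered whatever their observed correlation. Keep the Pearson correlations as description. State in advance which estimate leads.
3. If a smaller model is to be used for the SLIPS subset, name its covariates now.
4. Examine walking speed in a sensitivity analysis. Its recording is stated only for the STAMP walk, and it may itself be affected by neuropathy (a judgement, since section 9 lists it with the others).

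No new data are needed for the main model. The cost is precision, and the plan should say so: power of the adjusted model for a difference of 4 goes from 79% to 75-65% if the three covariates explain nothing and groups are 0.4-0.8 SD apart on each, with less loss or a gain if they explain a useful share. For 80% power in the worst of these cases the adjusted model needs 32-42 per group, against 29 unadjusted. The unadjusted comparison keeps its present power.

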## Secondary outcome analyses

- 1) Regional analysis: A masking algorithm will be utilised to map the previously defined areas of interest (Measured at the standard ten regions heel, mid foot, 1st MTH, 2nd MTH, 3rd MTH, 4th MTH, 5th MTH, hallux, second toe and toes 3-5) following data acquisition. Intergroup comparisons will be performed comparing mean peak plantar strain at each region using linear regression. Multiple regression analysis will be used to explore the relationship between correlated continuous variables and the risk group. This method will also be utilised to perform regional intergroup comparisons for peak PSS, peak plantar pressure and PTI.
- 2) Peak PSS between DFU and Low risk groups will be compared using linear regression. Bivariable analysis using Pearson's correlation coefficient will be performed to investigate the relationship between the continuous independent variables and mean peak plantar strain. Multiple regression analysis will be used to explore the relationship between correlated continuous variables and the risk group. This method will also be used to perform comparisons between groups for peak plantar pressure and PTI.
- 3) Multinomial regression analysis will be used to investigate the relationship between peak plantar strain and ulcer location.
- 4) ~~Regional analysis: A masking algorithm will be utilised to map the previously defined areas of interest (Measured at the standard ten regions heel, mid foot, 1st MTH, 2nd MTH, 3rd MTH, 4th MTH, 5th MTH, hallux, second toe and toes 3-5) following data acquisition. Intergroup comparisons will be performed comparing mean PSS at each region using ANCOVA, adjusting for factors matched..... Evidence of associated will be present if  $r > 0.3$ . Multiple regression analysis will be used including continuous variables with  $r > 0.3$ , risk group and the presence of joint deformity.~~

## **17. Data and monitoring**

### **17.1 Data collection**

All data will be collected and stored in accordance with Trust standards and procedures. When the data is collected it will be coded to pseudonymise the data. The patients' details and their coded data will be then separated and kept in the locations previously stated. The study database will be stored on a password-controlled computer in a locked access-controlled area in the Leeds General Infirmary. The patient files will be stored in a locked cabinet in a locked room in the Leeds Vascular Institute.

### **17.2 Data storage**

All data will be handled, computerised and stored in accordance with the Data Protection Act 1998.

## **18. Quality Assurance and Ethical Considerations**

### **18.1 Quality Assurance**

The study will be conducted in accordance with the principle of Good Clinical Practice (GCP) in clinical trials as detailed by the Medical Research Council (MRC), the NHS research Governance Framework (RGF) and Scottish Executive Health Department Research Governance Framework for Health and Social Care 2006.

### **18.2 Ethical considerations**

The study will be performed in accordance with the recommendations guiding physicians in biomedical research involving human subjects adopted by the 18th World Medical Assembly, Helsinki, Finland, 1964, amended at the 52nd World Medical Association General Assembly, Edinburgh, Scotland (1996 or later). Informed written/witnessed verbal consent will be obtained from the patients prior to inclusion into the study. The right of a participant to refuse

participation without giving reasons must be respected. The participant must remain free to withdraw at any time from the study without giving reasons and without prejudicing his/her further treatment. The study will be submitted to and approved by a main REC prior to entering patients into the study. The CI will provide the main REC with a copy of the final protocol, patient information sheets, consent forms and all other relevant study documentation.

## **19. Confidentiality**

Collection of patient data that includes patient identifiers will comply with all aspects of the Data Protection Act 1998. Any information that would allow individual patients or clinicians to be identified will not be released into the public domain.

All data will be collected and stored in accordance with Trust standards and procedures. When the data is collected it will be coded to pseudonymise the data. The patients' details and their coded data will be then separated and kept in the locations previously stated.

Computers that are used to store electronic data will be password protected. Paper copies of data will be kept in a locked filing cabinet in a locked room. All new data will be backed up at the end of each data collection session. Weekly back up of all the data set will be stored both on and off site securely. Patient's details will not be exposed to the public at any stage and kept securely under the research team.

## **20. Archiving**

At the end of the study, the data will be securely archived in line with Trust policy for 15 years. Following this, arrangements for confidential destruction will be made.

## **21. Statement of Indemnity**

As sponsor, the Leeds Teaching Hospitals NHS Trust does not provide indemnification against claims arising from non-negligent harm.

The NHS has a duty of care to patients treated, whether or not the patient is taking part in a clinical study. Therefore, clinical negligence indemnification will rest with the participating NHS Trust or Trusts under standard NHS arrangements under this duty of care.

## **22. Publication Policy**

The study will be registered with an authorised registry, according to the International Committee of Medical Journal Editors (ICMJE) Guidelines, prior to the start of recruitment.

The success of the study depends upon collaboration of all participants. For this reason, credit for the main results will be given to all those who have collaborated in the study, through authorship and contributorship. Uniform requirements for authorship for manuscripts submitted to medical journals will guide authorship decisions. These state that authorship credit should be based only on substantial contribution to:

- Conception and design, or acquisition of data or analysis and interpretation of data,
- Drafting the article or revising it critically for important intellectual content,
- And final approval of the version to be published,
- And that all these conditions must be met ([www.icmje.org](http://www.icmje.org))
